5.2.1 Delay of Study Vaccination

The following events constitute contraindications to administration of vaccine. If any of these events occur at the time scheduled for vaccination, then the subject may be vaccinated at a later date, within the window specified in the Schedule of Activities, or withdrawn from dosing at the discretion of the Investigator.

- Acute disease at the time of vaccination. Acute disease is defined as the presence of a moderate or severe illness with or without fever. Vaccination can occur in persons with a minor illness, such as diarrhea, mild upper respiratory infection with or without low-grade fever.
 - Fever is defined as oral temperature of $>37.8^{\circ}\text{C}$ (100.0°F) at the time of vaccination.
- If the subject received a non-study inactivated vaccine within 14 days or a live vaccine within 28 days of the scheduled study vaccine, then the study vaccine may be delayed to be given at least 15 days after the inactivated vaccine or 29 days after the live vaccine.

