Risks to subjects receiving the study products are expected to primarily involve mild to moderate injection site reactions, which have been observed in animal studies and are generally observed and expected for other IM-administered vaccines. These local reactions may consist of transient and dose-dependent pain, swelling, and erythema. Possible systemic reactions, which are also

transient, may include fever, fatigue, chills, headache, myalgias, nausea, diarrhea, and arthralgias. Moderate to severe, short-term diarrhea has been observed in a minority of persons aged 18-60 years who received the investigational GRT-R908 and GRT-R910 vaccines. In addition, other AEs that have been generally associated with approved IM administered vaccines have included mild hematological and clinical chemistry abnormalities, which are usually reversible.

The investigational vaccines should not be administered to individuals with a known hypersensitivity to any component of the study product. There is also a potential risk of hypersensitivity reactions following the administration of any study product.

Several animal studies with experimental whole-virus inactivated and subunit vaccines of other coronaviruses have shown enhanced immunopathology in a greater number of vaccinated animals compared to controls upon subsequent virus infection. These experimental vaccines often exhibited Th2-biased immune responses or elicited antibodies that had poor neutralizing activity against the virus. In preclinical studies of the Gritstone ChAd-S/SAM-S, a predominant Th1-focused immune response was observed.

The relevance of these observations in humans is unknown. Notably, most people during their lifetimes have likely been infected with one or more of the 4 endemic strains of human coronaviruses (hCoV 229E, NL63, OC43, and HKU1) that circulate globally and are responsible for 10-30% of mild to moderate upper respiratory tract infections. Despite the likelihood of cross-reactive antibody responses with poor functional activity, no evidence of enhanced CoV disease in humans has ever been reported.

There is limited experience with administration of a boost dose(s) following EUA/licensed COVID-19 vaccine(s), and it is possible that the boost dose(s) may be associated with more frequent or more severe adverse events.

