
5 SELECTION OF SUBJECTS AND STUDY ENROLLMENT AND WITHDRAWAL/DISCONTINUATION

Up to 135 men and non-pregnant women (17 for Stage 1 and up to 118 for Stage 2), aged 18 or older, who are in good health and meet all eligibility criteria will be enrolled at IDCRC sites participating in this trial. The target population should reflect the community at large at each of the participating IDCRC sites.

For Stages 1 and 2, recruitment of eligible participants will proceed if the candidate participant expresses no intention to seek an EUA/licensed COVID-19 vaccine at least until completion of the key follow-up timepoint (at least 1 month after the last study vaccination). The study investigator or staff will discuss with potential participants that de-identified antibody aggregate data will be shared with them during the conduct of the study. It will be explained to potential study participants that, in the absence of a clear immune correlate of protection, the aggregate data could be used to estimate how each study group is responding to the study products.

Subject Inclusion and Exclusion Criteria must be confirmed by a study clinician licensed to make medical diagnoses and listed on the Form FDA 1572 as the site PI or sub-investigator.

No exemptions are granted on Subject Inclusion/Exclusion Criteria in DMID-sponsored studies. Questions about eligibility will be directed toward the DMID Medical Officer.

Healthy adults will be recruited through IRB-approved advertising and screened through the participating institution's screening protocol to confirm eligibility requirements for participation. The following eligibility criteria will be used:

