7. Women of childbearing potential (WOCBP)* must plan to avoid pregnancy for at least 60 days after the last study vaccination and be willing to use an adequate method of contraception** consistently for 30 days prior to first study vaccine and for at least 60 days after the last study vaccine.

**Not sterilized via bilateral oophorectomy, tubal ligation/salpingectomy, hysterectomy, or successful Essure® placement (permanent, non-surgical, non-hormonal sterilization with documented radiological confirmation test at least 90 days after the procedure); still menstruating; or < 1 year has passed since the last menses if menopausal.*

***Acceptable methods of birth control include the following: oral contraceptives, injection hormonal contraceptive, implant hormonal contraceptive, hormonal patch, intrauterine device, spermicidal products and barrier methods (such as cervical sponge,*

diaphragm, or condom with spermicide), abstinence, monogamous with a vasectomized partner, non-male sexual relationship.

8. Women of childbearing potential must have a negative urine or serum pregnancy test within 24 hours prior to each study vaccination.
9. Vital signs within acceptable ranges:
 - Pulse >50 and ≤ 100 beats per minute
 - Systolic blood pressure (BP) ≤ 140 millimeters of mercury (mmHg)
 - Diastolic BP ≤ 90 mmHg
 - Oral temperature $<37.8^{\circ}\text{C}$ (100.0°F)
10. Clinical screening lab evaluations (white blood cell (WBC), hemoglobin (HgB), platelets (PLT), alanine aminotransferase (ALT), aspartate aminotransferase (AST), alkaline phosphatase (ALP), total bilirubin (T Bili), creatine kinase (CK), serum creatinine (Cr) and prothrombin time (PT)/partial thromboplastin time (PTT)) are within acceptable normal reference ranges at the clinical lab being used*.

**With the exception that ALT, AST, ALP, and creatinine values that are below the reference range will not be exclusionary as these values below reference range are clinically insignificant. Any other screening lab value outside the reference range that is thought to be clinically insignificant by a site investigator must be discussed with the DMID Medical Officer prior to enrollment.*

11. Must agree to genetic testing and storage of samples for secondary research.

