5.1.3 Subject Exclusion Criteria

Subjects eligible to participate in this trial must not meet any of the following exclusion criteria:

1. History of prior confirmed (PCR or antigen test positive) COVID-19 less than 112 days prior to enrollment.
2. Positive for anti-nucleoprotein SARS-CoV-2 specific antibody by enzyme-linked immunosorbent assay (ELISA) and had the history of upper respiratory illness (URI) compatible with COVID-19 during the 112 days prior to enrollment (seropositivity without a history of URI during the 112 days prior to enrollment will be considered remotely infected persons eligible for enrollment).
3. Positive nasal swab polymerase chain reaction (PCR) at screening.
4. Body mass index (BMI) $> 30 \text{ kg/m}^2$ for Stage 1 participants and BMI $> 35 \text{ kg/m}^2$ for Stage 2 participants.
5. Presence of medical comorbidities that would place the subject at increased risk for severe COVID-19*.

**Chronic kidney disease, chronic lung disease (including moderate-to-severe asthma), chronic heart disease (heart failure, coronary artery disease or cardiomyopathies), cerebrovascular disease, diabetes mellitus, chronic liver disease, sickle cell disease.*

6. Increased risk of occupational exposure to SARS-CoV-2 (healthcare workers and emergency response personnel)*.

**Applies to Stage 1 participants only.*

7. Prior receipt of an approved/licensed or investigational SARS-CoV-2 vaccine (including under EUA)*, approved or investigational adenovirus-vectorized vaccines**, or any other approved or investigational vaccine likely to impact the interpretation of the trial data.

**Exclusion of prior receipt of EUA/licensed COVID-19 vaccines applies to Stage 1 participants only.*

***With the exception of prior receipt of EUA Johnson & Johnson/Janssen Ad 26 COVID-19 vaccine which is permitted for Groups 8 and 12.*

8. On current treatment or prevention agents with activity against SARS-CoV-2.

9. Current smoking or vaping or history of smoking or vaping in prior year*.

**Applies to Stage 1 participants only.*

10. Breastfeeding, pregnant, or planning to become pregnant during the course of the study.

11. Participation in another research study involving receipt of an investigational product in the 60 days preceding enrolment or planned use during the study period.

12. Receipt or planned receipt of any live, attenuated vaccine within 28 days before or after study vaccination.

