13. Receipt or planned receipt of any subunit or killed vaccine within 14 days before or after vaccination.

14. Administration of immunoglobulins and/or any blood products within the three months preceding the planned administration of first study vaccination or at any time during the study.

15. Any confirmed or suspected immunosuppressive or immunodeficient state, including human immunodeficiency virus (HIV) infection, asplenia, recurrent, severe infections and chronic (more than 14 continuous days) immunosuppressant medication within the past 6 months (inhaled, ophthalmic, and topical steroids are allowed).

16. History of allergic disease or reactions likely to be exacerbated by any component of the vaccine, including urticaria, respiratory difficulty or abdominal pain (or any immediate

allergic reaction of any severity to polysorbate due to potential cross-reactive hypersensitivity with the polyethylene glycol component of the vaccine).

17. Any history of hereditary angioedema, acquired angioedema, or idiopathic angioedema.
18. Any history of anaphylaxis, including but not limited to reaction to vaccination.
19. Any history of severe allergic drug reaction.
20. History of cancer (except basal cell carcinoma of the skin and cervical carcinoma in situ).
21. History of serious ongoing, unstable psychiatric condition that in the opinion of the investigator would interfere with study participation.
22. Seizure in the past 3 years or treatment for seizure disorder in the past 3 years.
23. Bleeding disorder (e.g., factor deficiency, coagulopathy, or platelet disorder), or prior history of significant bleeding or bruising following IM injections or venipuncture or family history of bleeding disorder.
24. Recent (within the past 3 months) surgery, immobility, chronic infection, or head trauma that could increase the risks of thrombosis.
25. Suspected or known current alcohol abuse. Suspected or known drug abuse in the 5 years preceding enrollment.
26. Seropositive for HIV, hepatitis B surface antigen (HBsAg), or seropositive for hepatitis C virus (antibodies to HCV).
27. Have an acute illness* within 72 hours prior to study vaccination.

**An acute illness which is nearly resolved with only minor residual symptoms remaining is allowable if, in the opinion of the site PI or appropriate sub-investigator, the residual symptoms will not interfere with the ability to assess safety parameters as required by the protocol.*

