28. History of venous or arterial thrombosis or any known thrombophilic condition including heparin-induced thrombocytopenia (HIT) or family history of thrombosis.
29. History of myocarditis or pericarditis.
30. History of Guillain-Barré Syndrome (GBS).
31. Receiving heparin treatment or on medications associated with increased risk of bleeding or thrombosis.

32. Any other condition that in the opinion of the investigator would pose a health risk to the participant if enrolled or could interfere with evaluation of the trial vaccine or interpretation of study results.

5.2 Delay of Study Vaccination, Withdrawal from the Study, Discontinuation of Study Product, or Study Termination

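### Section 5.2.1 allows vaccination during an active minor illness that Exclusion 27 bars unless it is nearly resolved and will not interfere with safety assessment

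*Protocol*

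**What the plan says.** Section 5.2.1 makes acute disease at the time of vaccination a contraindication, but counts only illness of at least moderate severity as acute disease. It then adds: "Vaccination can occur in persons with a minor illness, such as diarrhea, mild upper respiratory infection with or without low-grade fever". It does not ask whether the illness is resolving or whether it would interfere with assessment, and it does not mention the eligibility criteria.

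Section 5.1.3, Exclusion 27, reads: "Have an acute illness* within 72 hours prior to study vaccination". It has no severity threshold. Its footnote allows an illness that is nearly over, provided the site investigator or sub-investigator believes the "residual symptoms will not interfere with the ability to assess safety parameters as required by the protocol".

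The status of the exclusions is explicit. Section 5.1.3 opens with "Subjects eligible to participate in this trial must not meet any of the following exclusion criteria", and the introduction to Section 5 says "No exemptions are granted on Subject Inclusion/Exclusion Criteria in DMID-sponsored studies".

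On temperature, Inclusion 9 in Section 5.1.1 ("Vital signs within acceptable ranges") requires an oral reading below 37.8 °C. Section 5.2.1 defines fever as a reading above 37.8 °C and leaves low-grade fever undefined.

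**The concern.** Two operative dosing rules cover the same visit and neither refers to the other. A coordinator who opens the section on delaying vaccination finds permission to proceed; one who opens the exclusion list finds a bar.

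For Day 1 the consequence is an eligibility deviation. Section 10.5 removes subjects found ineligible at baseline from the per-protocol population. The Safety Analysis Population and the mITT population are not defined that way, so the analytic loss is confined to the per-protocol set.

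The choice of example adds to the problem. Sections 8.1 and 8.1.1.1 list diarrhea as a solicited systemic reaction, and Table 2 makes the occurrence of solicited reactions a primary endpoint. Someone dosed while ill with diarrhea brings a pre-existing solicited symptom into that endpoint, in Stage 2 groups planned at 7 to 12 subjects.

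**Working it through.** No arithmetic applies. The check sets the two rules against the same subject at a Day 1 vaccination visit.

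| Subject on Day 1 | Section 5.2.1 | Section 5.1 criteria | Agree? |
|---|---|---|---|
| Active moderate illness | Contraindicated | Barred by Exclusion 27 | Yes |
| Mild illness, nearly resolved, judged non-interfering | Permitted | Permitted by the Exclusion 27 footnote | Yes |
| Mild diarrhea or mild respiratory infection, active, not nearly resolved | Permitted | Barred by Exclusion 27 | **No** |
| Mild illness, nearly resolved, but leftover symptoms would interfere | Permitted | Barred: footnote condition not met | **No** |
| Oral temperature exactly 37.8 °C | Not a fever | Fails Inclusion 9 | **No** |

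**Can the rules be read together?** Only by carrying the Section 5.2.1 definition of acute disease into Exclusion 27. The text does not do this. One rule speaks of acute disease and the other of acute illness. One looks at the time of vaccination and the other at the preceding 72 hours. Exclusion 27 also has its own, narrower exception, which would have little purpose if mild illness were already outside the exclusion.

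**Which rule prevails on Day 1?** Section 5.2.1 is permissive (vaccination can occur), while the exclusions are mandatory and without exemption. Section 6.2.1 also requires eligibility and vital signs to be checked before the first dose. The stricter rule therefore governs, and a dose given in reliance on 5.2.1 is a deviation.

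**What about Dose 2?** Here the text is less clear. Section 6.6.6 repeats the eligibility review before the second dose in Group 12, but Section 5.2.3 leaves new conditions that meet an exclusion to the site investigator's judgment. Section 5.2.1 already limits a delayed dose to the visit window, with withdrawal from dosing as the alternative. Group 12's Dose 2 window is Day 57 ± 3 days.

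**How wide is the temperature gap?** The two limits certainly differ only at exactly 37.8 °C. Because low-grade fever is undefined, it cannot be said whether 5.2.1 would admit readings above that.

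**The case against.** The strongest reply is that this is a wording inconsistency with several safeguards around it, and much of that reply stands.

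- **Baseline.** Section 7.1 requires a reactogenicity assessment before each vaccination, so diarrhea present at dosing would be recorded before the injection. That weakens the attribution worry. It does not settle whether later worsening is illness or vaccine.
- **Discretion.** Exclusion 32 covers any other condition that "could interfere with evaluation of the trial vaccine or interpretation of study results", and Section 5.2.2 allows removal after the first dose for conditions that would interfere with evaluating responses. These supply a non-interference test, but not the nearly-resolved condition.
- **Precedence.** Harm on Day 1 requires a site to overlook a numbered exclusion. That is true, but Section 5.2.1 invites it.

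Three stronger readings are tempting and should not be adopted.

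- **Halting rules.** A reader might infer that pre-existing illness will distort the pause and escalation rules, because their Grade 3 solicited-event triggers carry no relatedness condition. The sentinel rule in Section 8.5.1 needs the same Grade 3 event, lasting at least 24 hours, in two sentinels. A mild illness would have to worsen that far and be matched in another subject. The result is a pause and DSMB review, which errs toward safety. Section 8.1.6 needs three or more subjects and leads only to a steering-committee review. The missing relatedness condition belongs to those rules, not to 5.2.1.
- **Known signal.** Section 2.3.3 reports that "Moderate to severe, short-term diarrhea has been observed in a minority of persons aged 18-60 years" after the two SAM products. A reader might carry this over to every group still to be dosed. Groups 7 and 8 will not be opened, and the groups still open appear to be mainly over 60. Groups 13 to 15 receive GRT-C909, which is not a SAM product.
- **Late Dose 2.** A reader might think the protocol is silent on a second dose delayed beyond its window. Section 5.2.1 already answers this: a delayed dose is given within the window or the subject is withdrawn from dosing.

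**Conclusion.** The contradiction is real and narrow. It concerns a mild illness that is still active, or whose leftover symptoms would interfere with safety assessment, plus a boundary mismatch at exactly 37.8 °C. On Day 1 the exclusion controls, so following 5.2.1 produces a deviation and may bring a pre-existing solicited symptom into a primary safety endpoint.

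The effect cannot be quantified, because the protocol gives no frequency for vaccination visits that coincide with active mild illness. The conclusion assumes that acute illness in Exclusion 27 has its ordinary meaning, since the protocol does not tie it to the 5.2.1 definition. Given the baseline assessment and the investigator safeguards, the priority is minor: worth correcting because the text is wrong and cheap to repair, not because the trial's conclusions are in doubt.

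**What to change.** In Section 5.2.1:

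1. Make the minor-illness sentence expressly subject to Exclusion 27 (nearly resolved and non-interfering) and to Inclusion 9 (oral temperature below 37.8 °C).
2. For Dose 1, delete diarrhea and low-grade fever as unconditional examples of acceptable illness.
3. State whether the Exclusion 27 test applies at Dose 2.

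The first two changes cost an occasional delayed first dose. Section 6.1 gives a 30-day screening period and lets screening evaluations be repeated, so this is easily absorbed.

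The third is a real choice. Group 12 has 8 to 12 subjects and a ± 3 day window, and under 5.2.1 a second dose that cannot be given in the window is not given. A strict rule could therefore cost second-dose data in the only Stage 2 double-boost group still planned. Allowing a minor illness at Dose 2, with the pre-dose baseline recorded, may be defensible there, but the protocol should say so.

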5.2.2 Withdrawal from the Study or Discontinuation of the Study Product and Replacement

Subjects are free to withdraw from participation in the study at any time upon request, without any consequence.

A study subject will be discontinued from participation in the study if any of the following reasons occur prior to initial dosing:

- Request by the subject to terminate participation.
- Study non-compliance to protocol requirements that in the opinion of the participating site PI or appropriate sub-investigator poses an increased risk (e.g., missing safety labs) or compromises the validity of the data.
- Request of primary care provider or NIAID.

A subject may be removed from the study for the following reasons post initial dosing; however, whenever possible the subject should be followed for safety and immunogenicity evaluations per protocol:

- Subject becomes pregnant before receiving the second dose of vaccine.
- Study non-compliance to protocol requirements that in the opinion of the participating site PI or appropriate sub-investigator poses an increased risk (e.g., missing safety labs) or compromises the validity of the data.
- Lost to follow-up.
- If the subject met an exclusion criterion for participation in the study (either newly developed or not previously recognized) that precludes further vaccination.
- Request of primary care provider, the IRB, FDA, or NIAID.
- Medical disease or condition, or new clinical finding(s) for which further vaccination, in the opinion of the participating site PI or appropriate sub-investigator, might compromise the safety of the subject, interfere with the subject's successful completion of this study, or interfere with the evaluation of responses.
- If any AE, clinical laboratory abnormality or situation occurs such that continued participation in the study would not be in the best interest of the subject.
- The occurrence of a related SAE.

If the subject agrees, every attempt will be made to follow all AEs through resolution or stabilization.

The reason for subject discontinuation or withdrawal from the study will be recorded on the appropriate data collection form.

Subjects who withdraw, or are withdrawn from this study, or are lost to follow-up after signing the informed consent form (ICF) and administration of the study product will not be replaced if they are withdrawn for safety reasons.

Subjects who withdraw, or are withdrawn from this study, or are lost to follow-up after signing the ICF but before administration of the study product may be replaced. If 2 or more subjects in a single group are withdrawn after the first study vaccination and before the second study vaccination for reasons other than safety issues (e.g., are found to be newly infected with SARS-CoV-2 by COVID-19 PCR and/or serology at the time of the second vaccination), the protocol team will discuss and determine whether replacement subjects should be enrolled.

